7.5. Reporting Procedures

7.5.1. Adverse Event Reporting

Any AE that occurs during the participant's enrollment in the study will be recorded on the AE case report form. Pre-existing medical conditions or symptoms occurring prior to the initiation

of the study will not be reported as AEs, but an exacerbation of a pre-existing medical condition or symptom will be reported as an AE. Pain, neurological status, and functional impairment should be considered AEs when a participant's complaint for any of these symptoms results in an unscheduled visit and/or when a participant presents with a new or worsening symptoms as compared to a previous visit. All AEs will be followed until the event is resolved or considered to be stable.

IF an AE is ongoing when the participant completes the final visit, the AE will be followed until resolution or until 3 weeks after the final study visit has passed, whichever comes first. The study files must contain relevant source documents to confirm the occurrence of an AE and must be provided to the IRB upon request.

What Event is Reported	When is Event Reported	By Whom is Event Reported	To Whom is Event Reported
Fatal or life-threatening unexpected, suspected serious adverse reactions	Within 7 calendar days of initial receipt of information	Investigator	Local/Internal IRBStryker's Post Market Surveillance Team
		Sponsor or Designee	FDA (if IND study)
Non-fatal, non-life- threatening unexpected, suspected serious adverse reactions	Within 15 calendar days of initial receipt of information	Investigator	 Local/Internal IRBs/Institutional Officials Stryker's Post Market Surveillance Team
		Sponsor or Designee	 FDA (IND/Marketed Products) All participating investigators
Unanticipated adverse device effects	Within 10 working days of investigator first learning of effect	Investigator	Local/internal IRBsStryker's Post Market Surveillance Team
		Sponsor or Designee	FDA (if IDE study)
Unanticipated Problem that is not an SAE	Within 14 days of the investigator becoming aware of the problem	Investigator	 Local/internal IRBs/Institutional Officials Stryker's Post Market Surveillance Team
All Unanticipated Problems	Within 30 days of the IRB's receipt of the report of the UP from the investigator	IRB	• OHRP
		Investigator	• IRB

7.5.2. Serious Adverse Event Reporting

Describe the SAE reporting procedures, including timeframes. Include description and a flow chart of when events are reported to various oversight and regulatory groups, and what study staff are responsible for completing and signing off on the SAE reports. Describe who will receive notification of SAEs.

Generally, any AE considered serious by the PI or Sub-investigator or which meets the definition of an SAE included in **Section 8.1.2**, **Definition of Serious Adverse Event** must be submitted on an SAE form to the DCC if one exists for the study. If a study is overseen by a Data and Safety Monitoring Board (DSMB), the DSMB may request to receive real-time notification of all SAEs or only SAEs thought to be related to study agent.

According to 21 CFR 312.32(c)(1), "the sponsor must notify FDA and all participating investigators...in an IND safety report of potential serious risks, from clinical trials or any other source, as soon as possible, but in no case later than 15 calendar days after the sponsor determines that the information qualifies for reporting. The sponsor must report any suspected adverse reaction that is both serious and unexpected. The sponsor must report an adverse event as a suspected adverse reaction only if there is evidence to suggest a causal relationship between the drug and the adverse event, such as:

- A single occurrence of an event that is uncommon and known to be strongly associated with drug exposure (e.g., angioedema, hepatic injury, Stevens-Johnson Syndrome);
- One or more occurrences of an event that is not commonly associated with drug exposure, but is otherwise uncommon in the population exposed to the drug (e.g., tendon rupture);
- An aggregate analysis of specific events observed in a clinical trial (such as known consequences of
 the underlying disease or condition under investigation or other events that commonly occur in
 the study population independent of drug therapy) that indicates those events occur more
 frequently in the drug treatment group than in a concurrent or historical control group.

Furthermore, according to 21 CFR 312(c)(2, "the sponsor must also notify FDA of any unexpected fatal or life-threatening suspected adverse reaction as soon as possible but in no case later than 7 calendar days after the sponsor's initial receipt of the information."

As noted previously, an unanticipated adverse device effect could be considered an SAE (Section 8.1.2, Definition of Serious Adverse Event). For IDE studies, according to 21 CFR 812.150(a)(1), "an investigator shall submit to the sponsor and to the reviewing IRB a report of any unanticipated adverse device effect occurring during an investigation as soon as possible, but in no event later than 10 working days after the investigator first learns of the effect." In addition, 21 CFR 812.150(b)(1), "A sponsor who conducts an evaluation of an unanticipated adverse device effect under 812.46(b) shall report the results of such evaluation to FDA and to all reviewing IRB's and participating investigators within 10 working days after the sponsor first receives notice of the effect. Thereafter the sponsor shall submit such additional reports concerning the effect as FDA requests."

All deaths and immediately life-threatening events, whether related or unrelated, will be recorded on the SAE Form and submitted to the DCC/study sponsor within 24 hours of site awareness. See **Section 1**, **Key Roles** for contact information.

Other SAEs regardless of relationship, will be submitted to the DCC/study sponsor within 72 hours of site awareness

The study investigator shall complete an Unanticipated Adverse Device Effect Form and submit to the study sponsor and to the reviewing IRB as soon as possible, but in no event later than 10 working days after the investigator first learns of the effect. The study sponsor contact information is provided in **Section 1**, **Key Roles**. The investigator and study sponsor are responsible for conducting an evaluation of an unanticipated adverse device effect and shall report the results of such evaluation to FDA and to all reviewing IRBs and participating investigators within 10 working days after the sponsor first receives notice of the effect. Thereafter the sponsor shall submit such additional reports concerning the effect as FDA requests.

7.5.3. Unanticipated Problem Reporting

Incidents or events that meet the OHRP criteria for UPs require the creation and completion of an UP report form. It is the site investigator's responsibility to report UPs to their IRB and to the DCC/study sponsor. The UP report will include the following information:

- Protocol identifying information: protocol title and number, Pl's name, and the IRB project number;
- A detailed description of the event, incident, experience, or outcome;
- An explanation of the basis for determining that the event, incident, experience, or outcome represents an UP;
- A description of any changes to the protocol or other corrective actions that have been taken or are proposed in response to the UP.

To satisfy the requirement for prompt reporting, UPs will be reported using the following timeline:

- UPs that are SAEs will be reported to the IRB and to the study sponsor within 10 days the investigator becoming aware of the event.
- Any other UP will be reported to the IRB and to the DCC/study sponsor within 10 days of the investigator becoming aware of the problem.
- All UPs should be reported to appropriate institutional officials (as required by an
 institution's written reporting procedures), the supporting agency head (or designee),
 and OHRP within 10 days of the IRB's receipt of the report of the problem from the
 investigator.

An investigator shall submit to the sponsor and to the reviewing IRB a report of any unanticipated adverse device effect occurring during an investigation as soon as possible, but in no event later than 10 working days after the investigator first learns of the effect (21 CFR 812.150(a)(1)), A sponsor who conducts an evaluation of an unanticipated adverse device effect under 812.46(b) shall report the results of such evaluation to FDA and to all reviewing IRB's and participating investigators within 10 working days after the sponsor first receives notice of the effect. Thereafter the sponsor shall submit such additional reports concerning the effect as FDA requests (21 CFR 812.150(b)(1)).

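### Section 7.5 sets two deadlines for the same safety reports (14 or 10 days to the IRB, 30 or 10 days to OHRP) and does not say which prevails

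*Protocol*

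**What the plan says.** Three places in protocol section 7.5 set reporting deadlines.

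**Table in 7.5.1.**
- UP that is not an SAE, investigator to the IRB and to Stryker's Post Market Surveillance Team: "Within 14 days of the investigator becoming aware of the problem".
- All UPs, IRB to OHRP: "Within 30 days of the IRB's receipt of the report of the UP from the investigator".
- Fatal or life-threatening reactions that are unexpected and suspected to be related, investigator to the IRB and the Stryker team: "Within 7 calendar days of initial receipt of information".
- Other serious reactions of that kind, same route: "Within 15 calendar days of initial receipt of information".

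**Section 7.5.2.** Deaths and immediately life-threatening events, related or not: "will be recorded on the SAE Form and submitted to the DCC/study sponsor within 24 hours of site awareness". All other SAEs, again whatever their relationship to the device, have 72 hours to the same recipient.

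**Section 7.5.3.** For serious UPs: "UPs that are SAEs will be reported to the IRB and to the study sponsor within 10 days". For the rest: "Any other UP will be reported to the IRB and to the DCC/study sponsor within 10 days". Both run from the investigator's awareness. UPs also go to institutional officials, the supporting agency "and OHRP within 10 days of the" IRB's receipt of the investigator's report.

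The investigator's clock for an unanticipated adverse device effect is 10 working days in all three places.

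**The concern.** Some events have two deadlines for the same report, and the protocol has no order of precedence. A site that works from the table can report a non-serious UP on day 12, meet the table, and breach 7.5.3. Section 13.3 treats any noncompliance with the protocol as a deviation to be reported within 10 working days, so such a site could generate deviations without knowing it.

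Safety oversight depends on these reports. Section 7.7 puts it under the IRB, and the halting rule in 7.6 counts certain events once they have been reported to the IRB. Where a qualifying event falls in a class with two clocks, the longer one allows that count, and any halt, to come later.

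**Working it through.** No sample size, power or error rate is involved. The check sets the clocks side by side by event, recipient and start, and takes differences. Unqualified days are read as calendar days.

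**Step 1: same event, recipient and trigger.**

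| Report | Table, 7.5.1 | 7.5.3 | Difference |
|---|---|---|---|
| UP that is not an SAE, investigator to IRB, from awareness | 14 days | 10 days | 14 − 10 = 4 days |
| UP to OHRP, from IRB receipt | 30 days | 10 days | 30 − 10 = 20 days |

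Both are direct contradictions. In the OHRP row the table names the IRB as reporter and 7.5.3 names no reporter; the trigger and recipient are the same.

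**Step 2: serious events, to the sponsor.** Every reaction in the table's two serious rows is also covered by 7.5.2, because 7.5.2 takes all SAEs regardless of relationship. Some will also be UPs under 7.5.3.

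| Event | 7.5.2 | 7.5.3, if also a UP | Difference |
|---|---|---|---|
| Death or immediately life-threatening | 24 hours | 10 days | 10 − 1 = 9 days |
| Other SAE | 72 hours | 10 days | 10 − 3 = 7 days |

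If the Stryker surveillance team is the sponsor's recipient, the table adds a further clock: 7 days against 24 hours (7 − 1 = 6 days) and 15 days against 72 hours (15 − 3 = 12 days). Section 8 supports that reading: it assigns monitoring to the study sponsor and the IRB, then lists the activities of the IRB and of Stryker Spine. The table itself does not say so, and it has separate lines for the sponsor or its designee.

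**Step 3: serious reactions that are also UPs, to the IRB.**

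| Event | Table | 7.5.3 | Looser text |
|---|---|---|---|
| Fatal or life-threatening | 7 days | 10 days | 7.5.3, by 10 − 7 = 3 days |
| Other serious | 15 days | 10 days | Table, by 15 − 10 = 5 days |

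The direction reverses between the two rows.

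**Step 4: device effects.** 10 working days in 7.5.1, 7.5.2 and 7.5.3, so no difference.

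**Step 5: scale.** Section 5.3 expects 2 participants per month. Assuming a 30-day month, the number enrolled during a gap is 2 × gap ÷ 30: 4 days gives 0.27, 12 days gives 0.8, and 20 days gives 1.33.

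**The case against.** **The serious-event clocks may be meant to coexist.** Section 7.5.2 asks for an SAE form and 7.5.3 for a UP report form. A quick SAE notice followed by a fuller UP report would be an ordinary arrangement, and the table's serious rows cover a narrower class than 7.5.2. This has force. It is why Steps 2 and 3 are called overlapping clocks and not flat contradictions. The protocol does not state such a two-stage scheme, however.

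**Ten days might mean working days.** Ten working days are two five-day weeks, or 14 calendar days, which would remove the first conflict. But 7.5.3 writes working days explicitly for device effects and omits the word for UPs. The reading would not rescue 30 against 10 days for OHRP.

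**The effect is small.** At the planned accrual a gap of a few days spans less than one enrolment, and section 8 has the IRB reviewing reported adverse events monthly. This stands, and it limits the weight of the point.

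**Stronger readings that the protocol does not support.** A reader might infer that the site itself would be late in every conflicting row. The OHRP report is the IRB's in the table, so that row is not a site breach. A reader might also treat 7 days against 24 hours for deaths as a firm contradiction. It depends on identifying the Stryker team with the sponsor. Section 1, Key Roles, which might settle that, is not in the text available here.

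**Conclusion.** The inconsistency is real. Two conflicts are firm: 14 against 10 days to the IRB for a UP that is not an SAE, and 30 against 10 days to OHRP from the IRB's receipt. They assume only that unqualified days are calendar days, and for OHRP not even that. The serious-event clocks overlap by 3 to 12 days. The 7- and 9-day sponsor differences and the 3- and 5-day IRB differences apply only when the event is also a UP. The 6- and 12-day differences apply only if the Stryker team receives reports for the sponsor.

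It would be tempting to conclude that the table is the laxer text and only needs correcting. That does not follow, because for a fatal or life-threatening UP the table is the tighter one towards the IRB. Nor is taking the shorter of table and 7.5.3 a safe shortcut: for a non-fatal serious reaction that is also a UP, the shorter of 15 and 10 days still misses the 72-hour sponsor rule in 7.5.2 by 7 days.

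The consequence is a possible delay of days in safety reports to the IRB and sponsor, and up to 20 days to OHRP. No endpoint or analysis changes. It should be corrected because it concerns participant safety and costs little.

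**What to change.** Reconcile the 7.5.1 table with 7.5.2 and 7.5.3 so that each combination of event type, reporter and recipient has one deadline and one stated clock start. In doing so:

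- Keep the IRB's receipt as the start of the OHRP clock, on which both texts agree. A single start at site awareness would use up the IRB's time before it had the report.
- Separate the investigator's lines from the sponsor-to-FDA lines. The table's 7 and 15 days match the sponsor limits quoted in 7.5.2, so overwriting whole rows would create a new mismatch.
- Say whether the SAE form and the UP report are separate submissions, whether the Stryker surveillance team receives reports for the sponsor, and whether days are calendar or working days.
- Leave the device-effect clock as it is.

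The sponsor and the IRB decide which figures stand. The cost is a change of protocol wording, with the IRB approval that section 12.2 requires for any amendment, and possibly a tighter clock for the site or the IRB.

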7.6. Study Halting Rules

Implantation of the study devices will be halted when three grade 3 AEs determined to be "probably related" are reported to the IRB. The PI will notify the study sponsor and IRB immediately when the third grade 3 event is reported and the investigators will stop accepting new study participants.

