5.5. Premature Termination or Suspension of Study

This study may be temporarily suspended or prematurely terminated if there is sufficient reasonable cause. Written notification, documenting the reason for study suspension or termination, will be provided by the suspecting or terminating party to <investigator, funding agency, the IND/IDE sponsor and regulatory authorities>. If the study is prematurely terminated or suspended, the PI will promptly inform the IRB and will provide the reason(s) for the termination or suspension.

Circumstances that may warrant termination or suspension include, but are not limited to:

- Determination of unexpected, significant, or unacceptable risk to participants
- Demonstration of efficacy that would warrant stopping
- Insufficient compliance to protocol requirements
- Data that are not sufficiently complete and/or evaluable
- Determination of futility

Study may resume after concerns about safety, protocol compliance, and data quality are addressed and satisfy the sponsor, IRB and/or FDA

6. Study Procedures and Schedule

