7.1. Anticipated Adverse Events

^{**}For high-risk patients only

The following anticipated adverse events (AE) for study subjects are identical to any other patient implanted with the Tritanium PL or PEEK Cage, regardless of study participation.

7.1.1. Table 8.1.1.: Potential Adverse Events for Implantation of the Tritanium PL or PEEK Cage

Anticipated Adverse Events for Imp	plantation of the Tritanium PL Cage			
Late bone fusion	Peripheral neuropathies			
No visible fusion mass	Nerve damage			
Pseudarthrosis	Heterotopic bone formation			
Implant weakening	Neurovascular compromise, including paralysis, loss of bowel, bladder function, or foot-drop			
Superficial or deep-set infection	Spine growth cessation of the fused portion			
Inflammatory phenomena	Loss of proper spinal curvature, correction, height, and/or reduction			
Allergic reaction to implanted materials	Delayed union or nonunion			
Decrease in bone density due to stress shielding	Neurological and spinal dura mater lesions from surgical trauma			
Dural leak requiring surgical repair	Early loosening resulting from inadequate initial fixation, latent infection, premature loading of the device, or trauma			
Bone Erosion	Late loosening resulting from trauma, infection, biological complications or mechanical problems			
Pain	Distraction or stress shielding of the graft or fusion mass caused by inappropriate or improper surgical placement of device			
Intraoperative fissure, fracture, or perforation of spine	Postoperative fracture of bone graft or the intervertebral body above or below the level of surgery due to trauma, the presence of defects, or poor bone stock			
Spinal Surgery Complications				
Genitourinary Disorder	Gastrointestinal Disorder			
Vascular Disorder, including thrombus	Bronchopulmonary Disorder, including emboli			
Bursitis	Hemorrhage			
Myocardial infarction	Infection			
Paralysis	Death			

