7.3. Classification of an Adverse Event

7.3.1. Severity of Event

For AEs not included in the protocol defined grading system, the following guidelines will be used to describe severity.

- **Mild** Events require minimal or no treatment and do not interfere with the participant's daily activities.
- Moderate Events result in a low level of inconvenience or concern with the therapeutic measures. Moderate events may cause some interference with functioning.
- Severe Events interrupt a participant's usual daily activity and may require systemic drug therapy or other treatment. Severe events are usually potentially life-threatening or incapacitating.

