7.3.2. Relationship to the Study Device

For all collected AEs, the clinician who examines and evaluates the participant will determine the AE's causality based on temporal relationship and his/her clinical judgment. The degree of certainty about causality will be graded using the categories below.

Definitely Related – There is clear evidence to suggest a causal relationship, and other possible contributing factors can be ruled out. The clinical event, including an abnormal laboratory test result, occurs in a plausible time relationship to device implantation and cannot be explained by concurrent disease or other drugs or chemicals.

Probably Related – There is evidence to suggest a causal relationship, and the influence of other factors is unlikely. The clinical event, including an abnormal lab test result, occurs within a reasonable time after device implantation, is unlikely to be attributed to concurrent disease or other drugs or chemicals.

Possibly Related – There is some evidence to suggest a causal relationship (e.g., the event occurred within a reasonable time after device implantation). However, other factors may have contributed

to the event (e.g., the participant's clinical condition, other concomitant events). Although an AE may rate only as "possibly related" soon after discovery, it can be flagged as requiring more information and may be upgraded as appropriate

Unlikely to be Related – A clinical event, including an abnormal tab test result, whose temporal relationship to device implantation makes a causal relationship improbable (e.g., the event did not occur within a reasonable time after device implantation) and in which other drugs or chemicals or underlying disease provides plausible explanations (e.g., the participant's clinical condition, other concomitant treatments).

Not Related – The AE is completely independent of the study device implantation, and/or evidence exists that the event is definitely related to another etiology. There must be an alternative, definitive etiology documented by the clinician.]

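### The halting rule in Protocol 7.6 names only 'probably related' events, so as worded it does not count definitely related events toward the implantation halt

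*Protocol*

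**What the plan says.** Protocol section 7.6 has two sentences. The first sets the trigger: "Implantation of the study devices will be halted when three grade 3 AEs determined to be 'probably related' are reported to the IRB". The second requires the principal investigator to notify sponsor and IRB "immediately when the third grade 3 event is reported and the investigators will stop accepting new study participants". The second sentence does not repeat the causality condition.

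The terms come from two scales. Section 7.3.2 grades causality in five categories: Definitely, Probably, Possibly, Unlikely to be, and Not Related. The top category is described as "There is clear evidence to suggest a causal relationship, and other possible contributing factors can be ruled out" and the next as "There is evidence to suggest a causal relationship, and the influence of other factors is unlikely". Section 7.3.1 grades severity as Mild, Moderate or Severe, without numbers. It opens with "For AEs not included in the protocol defined grading system, the following guidelines will be used to describe severity", but no such grading system is set out in the protocol text at hand. Of the top level it says "Severe events are usually potentially life-threatening or incapacitating".

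**The concern.** The causality term in 7.6 stands in quotation marks and matches one label of the 7.3.2 scale. The examining clinician assigns a category to each event, so an event rated 'Definitely Related' is not rated 'Probably Related'. With no words such as 'or higher', the first sentence counts the second-strongest category and omits the strongest. A safety rule should not count the less certain device events and pass over the more certain ones.

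What is at stake is clarity at the moment when the rule has to be applied. A halting rule is useful because it removes argument. Here the people applying it would first have to agree that it means more than it says.

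**Working it through.** The protocol gives no operating characteristic for this rule and no adverse event rates, so there is no figure to reproduce. The check is a comparison of the text of 7.6 with the two scales.

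**Causality (7.6 against 7.3.2).** Categories on the scale: 5. Categories named in 7.6: 1 ('probably related'). Categories stronger than the one named: 1 ('Definitely Related'). Words in 7.6 that extend the named category upward: none.

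**Severity (7.6 against 7.3.1).** Levels on the scale: 3. Levels with a number: 0. Severe is the third of three ordered levels, so 'grade 3' most likely means Severe, but the protocol does not say so. The other numeric grades in the protocol describe spondylolisthesis.

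**Effect on the count.** Let b be the number of probably related grade 3 events and d the number of definitely related ones, all reported to the IRB.

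- First sentence as worded: implantation halts when b reaches 3, whatever d is.
- First sentence with 'probably or definitely related': implantation halts when b + d reaches 3.
- Example: b = 2 and d = 3 gives b + d = 5 related grade 3 events. The worded trigger is not met, because 2 < 3. The reworded trigger is met, because 5 ≥ 3.

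**Both sentences together.** What happens in the example depends on how each sentence is read:

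| Reading | Implantation | New enrolment |
|---|---|---|
| Both sentences strictly | Not halted by 7.6 (b = 2) | Stops at the third grade 3 event, whatever its causality |
| Both by context: 'probably' as a minimum, second sentence pointing back to the first | Halted at the third related event | Stops at the same event |
| First strictly, second by context | Not halted by 7.6 | Not stopped by 7.6 |

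On the strict reading of both sentences, the gap concerns only people already enrolled and waiting for surgery. Section 5.3 expects 2 participants per month, and section 6.1.3 places surgery within 30 days of randomization unless there is a medical reason to postpone. That gives roughly 2 per month × 1 month = about 2 people at any time.

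**The case against.** The strongest reply is that nobody would apply the rule this way. Section 7.3.2 describes an ordered scale of certainty, and on such a scale 'probably' reads naturally as a floor. For the gap to do harm, the investigator, the sponsor and the IRB would all have to decide that stronger evidence of device causation should not count. This stands as a statement of likely intent, and it is why the point is minor. It does not change the wording, which names one category and stops there.

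A reader might go further and infer that any number of definitely related severe events could accumulate with nothing in 7.6 stopping the study. The documents do not support that. The inference reads the first sentence strictly and the second by context. Read with the same strictness, the second sentence stops new enrolment at the third grade 3 event, whatever its causality. Read by context, both sentences cover definite events. Only the mixed reading in the last row of the table leaves both stops unmet.

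Other safeguards also exist. Section 5.5 lists "Determination of unexpected, significant, or unacceptable risk to participants" among the circumstances that may warrant stopping. Sections 7.2.4 and 7.4 provide for corrective action or suspension after an unanticipated problem. Section 7.5.2 sets 24-hour and 72-hour limits for reporting serious events to the sponsor, regardless of relationship. Section 8 commits the IRB to a monthly review of adverse events. An event on the anticipated list in 7.1, such as "Early loosening resulting from inadequate initial fixation, latent infection, premature loading of the device, or trauma", may fall outside the unanticipated-problem route, though a cluster could qualify because unexpected frequency is one of the criteria in 7.2.4. These steps make an unnoticed run of such events unlikely. They are discretionary or reporting steps, however, and none replaces the numeric trigger.

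**Conclusion.** The point holds in limited form. As worded, section 7.6 does not count 'Definitely Related' events toward the implantation halt, although a minimum of 'probably' is the likely intent. This is a minor wording correction to a safety rule and does not touch the primary endpoint, the randomization or the analysis.

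Two stronger conclusions are not supported. First, the undefined 'grade 3' does not make the rule unusable: Severe is the obvious candidate, and stating it is a clarification. Second, no size can be put on the risk. That would need a rate of severe related events and the share rated definite, and the protocol gives neither. The share could be small, since ruling out other contributing factors is a demanding standard after surgery. The conclusion rests only on the wording of 7.6 and 7.3.2.

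**What to change.** In the first sentence of 7.6, replace the quoted label with 'probably or definitely related'. In the second sentence, replace the reference to the third grade 3 event with 'the third such event'. Before the second change is made, the investigator, sponsor and IRB should confirm that the enrolment stop is meant to use the same related-event trigger. If a broader enrolment stop was intended, it should be written as a separate rule.

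As a secondary clarification, add to 7.6 that grade 3 means Severe as defined in 7.3.1, if the same parties confirm it. This needs their agreement because it fixes the severity threshold of the rule. The mention of a separate grading system in 7.3.1 should then be deleted, or the system supplied.

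The cost is a short amendment to two sentences in 7.6 and one phrase in 7.3.1, with IRB approval. It adds no data collection and no burden on participants.
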